2.1.3 Plecanatide Mechanism of Action and Pharmacology

Plecanatide (SP-304) is a peptide discovered and synthesized by Synergy Pharmaceuticals Inc. (hereinafter referred to as Synergy).

Plecanatide binds to the GC-C receptor expressed on epithelial cells that line the intestinal lumen. This binding of drug to the GC-C receptor stimulates the intracellular production of cyclic guanosine monophosphate, resulting in decreased Na^+ reabsorption through Na^+/H^+ exchange and activation of Cystic Fibrosis Transmembrane Conductance Regulator (CFTR) (Sindic, 2006)[8]. Activation of CFTR in turn enhances transepithelial efflux of chloride and bicarbonate ions and consequently fluid secretion into the intestinal lumen is stimulated. This fluid secretion is expected to facilitate BMs. Nonclinical data (in human colon carcinoma T84 cells and in animals) suggested potential therapeutic utility of orally dosed plecanatide in the treatment of CIC.

2.1.4 Clinical Experience in Adults

Plecanatide, marketed in the United States as Trulance[®], received FDA approval for the treatment of adults with Chronic Idiopathic Constipation (CIC) in January 2017 and approval for the treatment of adults with IBS-C in January 2018. In clinical trials for CIC completed to date, plecanatide has been found to be safe and well-tolerated. Plecanatide has been shown to increase the frequency of bowel movements (BMs) in patients with Chronic Idiopathic Constipation (CIC); effects on stool consistency and reduction of the time to first bowel movement were also seen. Patients with IBS-C were shown to have $\geq 30\%$ reduction in worst abdominal pain/discomfort and an increase of ≥ 1 complete spontaneous bowel movement (CSBM) over baseline, in the same week, for at least 50% of the 12 treatment weeks.

2.1.5 Clinical Experience in Adults with CIC and IBS-C

Plecanatide has been extensively evaluated in multiple clinical studies in adults with CIC and IBS-C. Two phase 1, single-dose studies in healthy volunteers have been completed; one with plecanatide doses ranging from 0.1 mg to 48.6 mg and a food-effect study with plecanatide 9 mg. The results showed plecanatide to be safe and well tolerated with minimal food effect. At very high doses, gastrointestinal (GI) adverse effects were observed. Three phase 2 dose-ranging studies were conducted in CIC and IBS-C patients looking at 0.3, 1, 3, and 9 mg plecanatide doses administered daily from 14 days to 12 weeks. Plecanatide continued to be safe and demonstrated statistically significant efficacy in durable overall CSBM responders (CIC) and overall responder rate (IBS-C) over placebo with maximum effect seen at the 3-mg plecanatide dose. Treatment-emergent AEs consisted of transient GI effects consistent with the drug's pharmacologic action. Phase 3 studies were conducted in two CIC and two IBS-C randomized, double-blind, placebo-controlled trials looking at plecanatide 3 and 6 mg administered daily for 12 weeks. These data showed a statistically significant CSBM durable overall responder rate (CIC) and overall responder rate (IBS-C) for both plecanatide doses over placebo and the doses were safe and well tolerated. Two open-label, long-term safety and tolerability studies were also completed with mean duration of study drug exposure of 167.4 days in the CIC population and 184.8 days in the IBS-C population. Treatment-emergent AEs both qualitatively and quantitatively were similar to those observed in prior double-blind 12-week plecanatide studies. A pediatric study in patients with CIC aged 12-18 years is currently underway.

On 19 January 2017 and 24 January 2018, the FDA approved plecanatide (Trulance[®], 3 mg dosage strength) for the treatment of CIC and IBS-C, respectively in adults. Approval was based on efficacy and safety data from 3182 adult patients (1733 CIC and 1449 IBS-C) who were enrolled in four double-blind placebo-controlled clinical trials and received placebo or 3 mg Trulance once daily for 12 weeks. Additional safety data are available from a total of 9615 patients enrolled in these four studies and two longer-term chronic therapy studies of up to 72 weeks. The most common adverse reaction (reported in at least 2% of Trulance treated patients and at an incidence greater than placebo) was diarrhea 5.0% and 4.3% in the Trulance group (CIC and IBS-C, respectively) and 1% in the placebo group for each indication. The majority of reported cases of diarrhea occurred within 4 weeks of treatment initiation. In the CIC population, severe diarrhea

was reported in 0.6% of Trulance-treated patients compared to 0.3% of placebo-treated patients and was reported to occur within the first 3 days of treatment. In the IBS-C population, severe diarrhea was reported in 1.0% of Trulance treated patients compared to 0.1% of placebo treated patients and occurred within the first day of treatment.

Discontinuations due to adverse reactions occurred in 4.0% and 2.5% of Trulance-treated patients and 2.0% and 0.4% of placebo-treated patients; the most common adverse reaction leading to discontinuation was diarrhea in 2.0% and 1.2% of Trulance treated patients and 0.5% and 0% of placebo treated (CIC and IBS-C, respectively).

A description of the clinical trials, safety, and efficacy information can also be found in the Investigator's Brochure.

2.2 OBJECTIVES

2.2.1 Primary Objective

To evaluate the safety and efficacy of once daily oral plecanatide for 4 weeks as treatment for the relief of symptoms associated with IBS-C in children ages 6 to < 18 years.

2.2.2 Secondary Objective

To estimate the pharmacokinetic (PK) parameters of plecanatide in this patient population (to the extent possible, since plecanatide is not expected to be absorbed).

2.2.3 Rationale for Dose Selection

Safety and efficacy data with plecanatide in adult CIC and IBS-C clinical trials performed to date has defined a safe and effective dose roughly in the range of 0.05 mg/kg to 0.1 mg/kg. Data suggest that children aged 4 years through 16 years appear to have a GC-C receptor density more reflective of a "mature" intestine (Cohen, 1988) [9]. Although safety of a particular dose cannot be taken for granted, it is more likely that children in this age group will respond to a GC-C agonist similarly to adult patients. Thus, the expectation is that ≤ 0.05 mg/kg should represent safe and effective doses for treatment of IBS-C in children ages 6 to less than 18 years under study in this protocol. There are few data that might shed light on potential physiological differences between adults and children in terms of pharmacological dose-responsiveness to GC-C agonists.

Based on considerable PK experience in the adult population it is known that plecanatide is essentially unabsorbed from the human GI tract in the dose range proven effective for the treatment of adult CIC and IBS-C. There is no expectation that pediatric patients will differ in this respect. Therefore, the doses selected for an adolescent population are anticipated to be safe and well tolerated.

2.3 RISK-BENEFIT ASSESSMENT

The most common TEAEs in adult patients treated with plecanatide have been diarrhea and other gastrointestinal (GI)-related symptoms such as abdominal cramps, gas, and bloating (Investigator Brochure (IB) Ed. 9.0 for Plecanatide, 02/28/2018). It is expected that the plecanatide safety profile observed in the 6 to < 18-year old pediatric population will be similar to that observed in adult patients with CIC and IBS-C.

The amount of blood to be drawn during the course of this study (approximately 42 mL for the majority of patients, and 66 mL for patients participating in the intensive PK analysis) is not considered to be a risk to child and adolescent patients qualified for enrollment in this study.

2.4 CRITERIA FOR EVALUATION OF THE STUDY

The efficacy and safety endpoints are described below. For information concerning the analyses of these endpoints, see **Section 8.8** and **Section 8.10** respectively.

2.4.1 Efficacy Endpoints

2.4.1.1 Primary Efficacy Endpoint

The primary efficacy endpoint is the change from baseline in weekly SBM frequency over the 4 Week Treatment Period compared to placebo.

2.4.1.2 Secondary Efficacy Endpoints

The secondary efficacy endpoints are:

- Change from baseline in frequency and severity of abdominal pain and abdominal discomfort
- Change from baseline in frequency of BMs, SBMs, and CSBMs
- Time to First BM
- Change from baseline in stool consistency (BSFS or mBSFS-C)
- Use of Rescue Medication
- Change from baseline in frequency of fecal incontinence
- Change from baseline in frequency and severity of defecation pain
- Change from baseline in frequency of large diameter stools

2.4.1.3 Patient Reported Outcomes

The following patient reported outcomes will be assessed (see **Appendix I** for the assessment instruments used for these endpoints):

- Global IBS-Disease Severity
- Health-Related Quality of Life (KINDL® -QoL)
- Global Relief of IBS Symptoms
- Global Relief of Abdominal Pain
- Treatment Continuation Assessment
- Treatment Satisfaction Assessment

2.4.2 Pharmacokinetic Endpoints

Single dose and steady state PK of plecanatide and its major metabolite SP-338 (population modeling):

- Plasma concentration of plecanatide and SP-338 (Note: measurable plecanatide/SP-338 levels have not been observed in the adult population)
- PK parameters, including C_{max} , T_{max} , and C_{min} (only if sufficient number of plecanatide levels can be measured to allow computation of these parameters)

2.4.3 Safety Endpoints

The following safety endpoints will be assessed:

- Frequency of treatment-emergent adverse events (TEAEs)
- Withdrawals due to adverse events and serious adverse events

Clinically important changes in laboratory tests and vital signs will be presented.

2.5 JUSTIFICATION OF THE STUDY DESIGN

This is a randomized, double-blind, placebo-controlled, parallel group, Phase 2b study evaluating plecanatide 4-week treatment in child and adolescent patients with IBS-C.

Randomization and double-blind components of the study design are used to minimize bias in treatment group assignment and investigator/study personnel/patient bias, respectively, during the study. The fixed dose and time on study drug are the most objective ways to assess the therapeutic effect and safety of an investigational agent relative to placebo. The treatment period is 4 weeks, which is sufficient time to test the durability of response.

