8.8.1.1 Analysis of the Primary Efficacy Endpoint

The weekly SBM rate for each patient will be computed, as described in **Section 8.4.1**, for each week of the 4-week treatment period. The change from baseline in mean weekly SBM rate will be analyzed using a linear mixed-effects model with fixed effects for gender (stratification variable), treatment, week, and the corresponding baseline value; a random intercept for patient will also be specified. The least squares (LS) mean change from baseline will be presented, by treatment group, and the difference in LS means for each treatment group, A, B, and A and B combined, versus Placebo, with 95% confidence intervals and corresponding statistical *p*-values.

The above analysis will be repeated for the PP Population.

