8.8.2.2 Change from Baseline in Frequency of BMs, SBMs, and CSBMs, by Study Week

The weekly BM rate for each patient will be computed, as described in **Section 8.4.1**, for each week of the 4-week treatment period and for the two weeks of the follow-up period. A summary, by treatment group, of the mean weekly BM rate, and change from baseline in mean weekly BM rate, for each of the 6 study weeks will be presented. The change from baseline in mean weekly BM rate will be analyzed using a linear mixed-effects model with fixed effects for gender (stratification variable), treatment, week, the interaction of treatment and week, and the corresponding baseline value; a random intercept for patient will also be specified. The least squares (LS) mean change from baseline will be presented, by treatment group, and the difference in LS means for each treatment group, A, B, and A and B combined, versus Placebo, with 95% confidence intervals and corresponding statistical p-values.

Similarly, for the change from baseline in frequency of SBMs and CSBMs by study week.

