5.2.2. Primary Efficacy Analysis

The weekly SBM rate for each subject will be computed for each week of the 4-week treatment period. The change from baseline in mean weekly SBM rate will be analyzed using a linear mixed-effects model with fixed effects for gender (stratification variable), treatment, week, the interaction of treatment and week, and the corresponding baseline value; a random intercept for subject will also be specified. The least squares (LS) mean change from baseline will be presented, by treatment groups, and the difference in LS means for each treatment group versus placebo and combined active doses within each age group versus placebo in a separate model for each age group, and overall active doses versus placebo in a separate model with 95% confidence intervals and corresponding statistical p-values.

The baseline SBM weekly rate will be the weekly average number of SBMs recorded during each of the 2 weeks preceding initiation of study drug.

The above analysis will be repeated for the PP Population.

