5.2.3. Secondary Efficacy Endpoints

- Change from baseline in frequency and severity of abdominal pain and abdominal discomfort
- Change from baseline in frequency of BMs, SBMs, and CSBMs
- Time to First BM
- Change from baseline in stool consistency (BSFS or mBSFS-C)
- Use of Rescue Medication
- Change from baseline in frequency of fecal incontinence
- Change from baseline in frequency and severity of defecation pain
- Change from baseline in frequency of large diameter stools

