5.2.4.2. Change from Baseline in Frequency of BMs and CSBMs, by Study Week

The weekly BM (and CSBM) rate for each subject will be computed, as described in [Section 3.3.7](#), for each week of the 4-week treatment period and for the two weeks of the follow-up period. A summary, by treatment group, of the mean weekly BM (and CSBM) rate and change from baseline in mean weekly BM (and CSBM) rate, for each of the 6 study weeks will be presented. The change from baseline in mean weekly BM (and CSBM) rate will be analyzed using a linear mixed-effects ANCOVA model with fixed effects for gender (stratification variable), treatment, week, the interaction of treatment and week, and the corresponding baseline value; a random intercept for subject will also be specified. The least squares (LS) mean change from baseline will be presented, by treatment groups, and the difference in LS means for each treatment group versus placebo and combined active doses within each age group versus placebo in a separate model for each age group, and overall active doses versus placebo in a separate model with 95% confidence intervals and corresponding statistical p-values.

The baseline BM (and CSBM) rate will be calculated as the average BM (and CSBM) rate for each of the two weeks preceding initiation of study drug.

The above analysis will be repeated for the PP Population.

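### Four weeks is justified as a test of durability, but no durability contrast is defined, and the SAP omits, without saying so, the protocol's by-week and follow-up analysis of spontaneous bowel movements (SBMs)

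*Combined protocol and SAP*

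**What the plan says.** Protocol Section 2.5 gives this reason for the treatment length: "The treatment period is 4 weeks, which is sufficient time to test the durability of response". The primary endpoint is a change over the whole period: "The primary efficacy endpoint is the change from baseline in weekly SBM frequency over the 4 Week Treatment Period compared to placebo" (protocol Section 2.4.1.1).

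The protocol's primary model (Section 8.8.1.1) has "fixed effects for gender (stratification variable), treatment, week, and the corresponding baseline value; a random intercept for patient will also be specified". It contains no treatment-by-week term. The by-week view comes from Section 8.8.2.2, which describes a BM analysis over four treatment and two follow-up weeks, with a treatment-by-week interaction, and then adds: "Similarly, for the change from baseline in frequency of SBMs and CSBMs by study week".

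The SAP lists the secondary endpoint as "Change from baseline in frequency of BMs, SBMs, and CSBMs" (Section 5.2.3). The matching analysis section, 5.2.4.2, is headed "Change from Baseline in Frequency of BMs and CSBMs, by Study Week", and its text covers only those two variables. SBM appears in the primary analysis (SAP Section 5.2.2), which adds the treatment-by-week interaction but stops at Week 4: "The weekly SBM rate for each subject will be computed for each week of the 4-week treatment period". SAP Section 9.1 plans by-week SBM rate tables for the FAS and PP populations (14.2.2.1.X and 14.2.2.2.X). SAP Section 7, on changes to the planned analyses, does not mention SBM.

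**The concern.** Durability is a statement about time course: whether the effect seen early is still present at Week 4 and, on a wider reading, what happens after the last dose. An average over four weeks does not answer that. Protocol Section 8.8.2.2 was the place where SBM, the primary variable, would have been followed week by week and off treatment. The SAP keeps the endpoint in its list but gives it no analysis there, and does not say why.

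The SAP also treats some secondary variables more fully than the primary one. For abdominal pain and discomfort scores, stool consistency and defecation pain scores it asks for LS-mean differences at each week as well as across all four. For SBM it does not.

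At stake is whether the report can support any pre-specified statement on persistence of the SBM effect. If weekly or off-treatment SBM comparisons are chosen after unblinding, they will be post hoc.

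**Working it through.** **Side by side**

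- Durability: asserted in protocol Section 2.5. No primary, secondary or patient-reported endpoint in either document defines it, and no contrast between weeks is named.
- SBM by week, on treatment: planned in protocol Section 8.8.2.2; absent from SAP Section 5.2.4.2. It remains estimable from the interaction in SAP Section 5.2.2, but reporting of weekly differences from placebo is not requested.
- SBM in Weeks 5 and 6: planned in protocol Section 8.8.2.2; no comparison with placebo is specified anywhere in the SAP.
- Record of the change: none in SAP Section 7.

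**The plan's own figure**

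Inputs (protocol Section 8.2): 102 plecanatide and 34 placebo patients, difference 1.5 SBM/week, SDs 3.5 and 2.3. The significance level is taken as 0.05 two-sided, from protocol Section 8.4.

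SE = √(2.3²/34 + 3.5²/102) = 0.525. Power = Φ(1.5/0.525 − 1.96) = 81.5%, which matches the stated power. At the planned Group B size (90 active, 30 placebo), SE = √(2.3²/30 + 3.5²/90) = 0.559 and power is 76.5%.

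**What a persistence contrast could show**

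The contrast is (Week 4 − Week 1) on active minus the same on placebo. Assumptions: the SDs above apply at each week, and the between-week correlation ρ is the same in both arms. The documents give no ρ, so a range is used.

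SE = √[2(1 − ρ)] × √(2.3²/30 + 3.5²/90) = √[2(1 − ρ)] × 0.559

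Power = Φ(loss/SE − 1.96). For Group B, all active doses (90) against placebo (30):

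| ρ | SE | 95% CI half-width | Power, loss of 0.75 | Power, loss of 1.5 |
|---|---|---|---|---|
| 0.3 | 0.661 | 1.30 | 20% | 62% |
| 0.5 | 0.559 | 1.10 | 27% | 77% |
| 0.7 | 0.433 | 0.85 | 41% | 93% |
| 0.8 | 0.354 | 0.69 | 56% | 99% |

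Over the same range of ρ, power for a loss of 0.75 is 13% to 34% for one Group B dose (30 against 30), and 34% to 82% for all active against all placebo (150 against 60).

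**Two distortions to handle**

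- Zeros after withdrawal. SAP Section 3.3.4 sets SBM to 0 for weeks after a patient leaves. Apparent loss of effect = excess dropout on active × mean SBM among those who stay. With an assumed mean of 3 to 6 per week, a 5-point excess gives 0.05 × 3 = 0.15 to 0.05 × 6 = 0.30; a 10-point excess gives 0.30 to 0.60. Excess dropout on placebo works the other way and would hide waning.
- Length of Week 6. SAP Section 3.3.6 defines it as Days 36 to 49, which is 14 days, while the weekly rate is a sum (SAP Section 3.3.7). If diaries end on Day 42, the window holds 7 days and there is no inflation. If they run to Day 45, the end of the visit window, it holds 45 − 36 + 1 = 10 days, and the count can be up to 10/7 = 1.43 times a 7-day count.

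**The case against.** The strongest reply is that the SAP appears to have merged two SBM analyses. Its primary model has the treatment-by-week structure that protocol Section 8.8.2.2 planned for SBM, by-week SBM tables are listed, and a listing (16.2.6.2.1) gives derived weekly SBM values. For Weeks 1 to 4 this largely stands, and it rules out several stronger readings.

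- A reader might infer that waning of the SBM effect cannot be assessed. Weekly differences of 3, 2, 1 and 0 do average 1.5, the same as a constant 1.5, but that pattern is invented and the interaction model would tell the two apart. Protocol Section 8.2 also states the 1.5 difference as at four weeks; if that means Week 4, a pattern ending at 0 contradicts the design assumption.
- A reader might infer that the follow-up SBM data go unused. The SBM table titles have the same form as those for BM and CSBM, whose summaries cover six weeks, so the tables may include Weeks 5 and 6. The shells are not in the documents. What is missing is a specified comparison.
- A reader might infer that the follow-up diary exists to test SBM rebound, or that the design cannot address persistence. No text gives the diary that purpose, and daily placebo-controlled data are collected throughout. BM and CSBM are analysed in Weeks 5 and 6.
- The adult IBS-C response, required "in the same week, for at least 50% of the 12 treatment weeks" (protocol Section 2.1.4), describes other trials and is not a standard adopted here.

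Two limits to the reply remain. Estimability depends on the SAP's model, whereas protocol Section 8 says the primary analysis will stay as the protocol describes it, and that version has no interaction. And a table title does not specify a contrast with placebo.

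**Conclusion.** The concern holds as a specification gap. Followed as written, the SAP omits a secondary SBM analysis that the protocol planned, keeps the endpoint in its list, and does not disclose the omission. The durability rationale is left without a defined contrast, a requested weekly SBM difference from placebo, or a specified off-treatment SBM comparison.

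The gap does not bias the primary estimate or make on-treatment waning inestimable. Its practical size is that persistence statements about SBM would rest on choices made after the fact, from estimates of limited precision: in Group B a 95% CI half-width of 0.69 to 1.30 SBM/week, and 20% to 56% power for loss of half the design effect. Those figures assume the design SDs at each week and between-week correlations of 0.3 to 0.8. They support presenting the result as an estimate, not a test. The gap should be closed before unblinding.

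**What to change.** 1. Restore SBM to SAP Section 5.2.4.2 for Weeks 1 to 6, or record and justify its removal in SAP Section 7.
2. State that SBM LS-mean differences from placebo, with 95% CIs, will be reported for each of Weeks 1 to 4. Name Week 4, together with Week 4 minus Week 1, as the persistence estimate. Report Weeks 5 and 6 separately as the off-treatment result. This text is needed in addition to step 1, because Section 5.2.4.2 does not explicitly ask for week-specific differences even for BM and CSBM. Present all of these as estimates.
3. For the follow-up result, use a 7-day Week 6 window or scale per diary day. Add an observed-data version of the weekly SBM results beside the version with zeros after withdrawal.
4. Reword protocol Section 2.5 to refer to short-term (4-week) response, or define durability there by the Week 4 contrast.

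The cost is wording and a few extra estimates from diary data already collected. Weeks 1 to 4 come from the model already in SAP Section 5.2.2; Weeks 5 and 6 need the six-week analysis in protocol Section 8.8.2.2. The drawback is more unadjusted estimates in a trial that already adjusts none.
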